Potential participants will be identified from the haematology and melanoma late effects clinics, or other specialist clinics at Peter MacCallum Cancer Centre by a member of the nursing, medical or allied health teams. There will also be a REFRESH project information postcard (Appendix B) made available to patients from nursing staff. The REFRESH project information postcard has information about the project and a method for participants to make direct contact with the research team should they be interested in participating.

The research team will gain access to potential/interested participants via two main routes: a) a potential participant will make direct contact with the research team (via the details on the postcard) or b) a member of the PMCC medical or allied health team will identify potential participants; those who have reported to staff that they are struggling with fatigue and/or self-describe their fatigue as orange-red on the fatigue scale lanyard screening tool carried by nursing staff.

A process for recording the consent to share contact details with the research team has been developed. Nursing staff will enter a note into EPIC documenting the following: 'patient x has noted that they are happy to be contacted about the REFRESH study and have consented to having their contact details passed on to a member of the REFRESH study team'. This EPIC note will be cc'd to either [name] or [name] and will appear in the research study EMR/EPIC inbox, whereby the research team can make contact and commence the study consent and screening process.

After discussions with lead nursing specialists from the haematology and melanoma late effects clinics, we are expecting that the majority of potential participants will be identified via route 2 and there is significant confidence from staff that recruitment sample will be readily achieved.

REFRESH: Finding New Energy after Cancer

Eligibility Screen

A member of the research team will contact the participants by phone to explain the project and screen for eligibility using a screening eligibility checklist (see Appendix A.1).

Specifically;

- A series of fatigue questions will be administered to assess levels of fatigue, duration and impact of fatigue. These screening questions were chosen to be feasible in usual care.

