Cost	The resource cost of delivering the program per user	This self-help CBT program is expected to provide therapy at a lower cost compared to face to face, enabling more users to benefit	Booklet cost and records of therapist / administration time per person enrolled (Table 3)
Feasibility	The extent to which stepped care approach to CBT can be used for cancer fatigue	A majority of participants complete Step 1 in 6 weeks and/or Step 2 in 4 sessions	Phone surveys TQ1-A & TQ2-A include number of modules/sessions completed (dose)
Fidelity	The degree to which the program was implemented as intended (Proctor et al., 2011)	The adherence and deviations to program contacts and stepped care protocol	Field notes maintained by researchers

² Online or paper survey if preferred

REFRESH: Finding New Energy after Cancer

Intervention impact	Definition	Rationale	Method of evaluation
Fatigue	A distressing, persistent, subjective sense of physical, emotional and/or cognitive tiredness or exhaustion related to cancer and/or cancer treatment (National Comprehensive Cancer Network, 2020)	The program aims to reduce fatigue	Functional Assessment of Impact of Chronic Illness Therapy – Fatigue (FACIT-F) subscale (Cella, Eton, Lai, Peterman, & Merkel, 2002) will be used to determine progression to Step 2 and change in fatigue (online survey T1Q-B and TQ2-B).
Self-efficacy	A person's belief in their capacity to do what is necessary to produce specific performance attainments (Bandura, 1977)	Self-efficacy may be a mediator of health behaviour	Online surveys T0Q T1Q-B and T2Q-B. Perceived self-efficacy for fatigue self-management scale (PSEFSM) (Hoffman et al., 2011)
Health-Related Quality of Life	A multidimensional concept of the influence of health states on the extent to which a person is healthy, comfortable and able to participate in society	A brief appraisal of overall quality of life before and after program	EuroQual 5 Dimension 5 Level Scale (EQ-5D-5L) (Rabin & de Charro, 2001)
Personal, social and lifestyle factors	Certain modifiable factors can maintain fatigue. The program targets sleep, mood, distress, energy use and engagement in physical, social and leisure activities.	The aim of the CBT intervention is to alter behavioural and cognitive factors that perpetuate fatigue	Online surveys T1Q-B and T2Q-B

REFRESH: Finding New Energy after Cancer

Intervention Appropriateness

Intervention appropriateness for participants will be measured by

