- b. Intervention satisfaction will be assessed by administering the Client Satisfaction Questionnaire (CSQ) (Attkisson & Zwick, 1982). The CSQ is a well validated 8-item measure of the quality of the intervention, the extent to which the program met participant's needs, perceived increases in skills, and whether participants would recommend the program to others. Total scores range from 8 to 56, with higher scores indicating greater satisfaction. The CSQ will be administered in the T1Q-B and T2Q-B assessments where applicable (appendix A.4 and A.5).
Intervention satisfaction will also be evaluated in part A of the administered questionnaires (T1Q-A and T2Q-A) with open ended items such as "Is there anything you particularly liked or disliked about Chapter 2?" or "Did you find the week 5 phone call helpful?" (see Appendix A.3 and A.5); items designed to elicit participants' own perceptions about their satisfaction with the self-management booklet and the individual CBT sessions (if applicable).
- c. Rate of recruitment to / enrolment in program will contribute to evaluation of acceptability. Numbers of referrals received, eligible and enrolled participants, withdrawals and reasons for decline/ withdrawal) will be recorded in a spreadsheet to enable calculation of rates of program uptake, dropouts and factors related to non-participation.

Cost of Intervention Delivery (Clinical Feasibility)

Intervention procedures and costs will be evaluated by documenting and measuring the different activities employed to implement the intervention (e.g., direct and indirect therapy time (includes phone support and notes) x hourly rate), time taken to complete activities x hourly rate of clinician, in addition to costs of materials and program administration time per participant (e.g. screening, scheduling) x AHA hourly rate. (Does not include study related tasks e.g. information and consent). See Table 2.

Table 2: Clinical Feasibility: Intervention Procedures and Costs

Activity	Variables	Data Collected	Cost p/Unit
Screening	
 Initial screening by existing staff Stage 2 screening via checklist implementation 	
 Role of person screening. Time taken for initial screen 	

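### Screening is costed per participant at a single AHA rate, which conflicts with who does the screening, and the cost table has no explicit time item for the second-stage checklist and no rule for people screened but not enrolled

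*Protocol*

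**What the plan says.** **Costing rule.** The section Cost of Intervention Delivery (Clinical Feasibility) prices "program administration time per participant (e.g. screening, scheduling) x AHA hourly rate". The same sentence has a separate term, "time taken to complete activities x hourly rate of clinician". The only work it sets aside is study-related, with information and consent as the example, so screening stays in the cost.

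**Outcome and unit.** The Cost row of the evaluation overview (the first table labelled Table 2) defines the outcome as "The resource cost of delivering the program per user" and gives its source as "Booklet cost and records of therapist / administration time per person enrolled (Table 3"). The costs table is in fact the second table labelled Table 2.

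**Who screens.** Under Recruitment processes, potential participants are identified "by a member of the nursing, medical or allied health teams". Under Eligibility Screen, "A member of the research team will contact the participants by phone to explain the project and screen for eligibility". The Appendix A measures summary lists the checklist at 18 items and marks it as for clinicians only.

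**What is recorded.** The first Screening row of the costs table lists two activities: "Initial screening by existing staff" and a second-stage screen by checklist. The data collected are the screener's role and "Time taken for initial screen". The unit-cost column is blank. A later Screening row, for the end of the 5 weeks, has its own time item.

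**Who does not enrol.** People with mild fatigue are told that they are ineligible, the exclusion criteria are applied at a clinical screening interview, and people who decline are directed to online resources. Numbers referred, eligible and enrolled, and reasons for decline, are logged under Intervention Acceptability.

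**The concern.** Aim 2 covers the cost of implementing REFRESH in a clinical setting, and the Data Analysis section counts costs among the main feasibility outcomes. Screening precedes every enrolment, so an error in its cost enters the cost of every user.

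Three features pull the screening cost away from what a service would pay:

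- The text fixes one rate for work that the protocol assigns to several kinds of staff.
- The second-stage phone checklist has no time item of its own.
- Time is tied to participants or enrolled people, with no instruction for time spent on those who do not enrol.

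The rate can be changed at analysis. Minutes not logged during the study cannot be recovered.

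**Working it through.** The protocol states no cost, hourly rate, screening time or screen-to-enrol ratio, so there is no figure to reproduce. The check compares the sections and then illustrates the possible size.

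**1. Rate against role.** The formula names screening as an example of AHA-rate work and keeps the clinician rate as a separate term. The first screen is done by clinic staff of several professions. The second is done by a research team member, using a checklist reserved for clinicians, and eligibility also requires picking out a probable sleep disorder, psychosis, marked distress and risk of self-harm. The costs table records who screened, but the AHA term makes no use of it.

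**2. Activities against time items.**

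| Screening activity in the costs table | Time item |
|---|---|
| Initial screen by existing staff | yes |
| Second-stage checklist | none named |
| Re-screen at the end of 5 weeks | yes |

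**3. Numerator against denominator.** A cost per user needs the time spent on everyone screened, divided by the number enrolled. The protocol shows that some people screened will not enrol. The referral log supplies head counts, not minutes, and is not linked to the costing.

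**4. Illustrative size.** Assume equal screening time per person, and that the plan costs enrolled people only, at the AHA rate. Then

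factor = (number screened / number enrolled) × (screener's hourly rate / AHA hourly rate).

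The number enrolled is 50 (Participants section). The enrolment fractions and rate ratios are assumptions. The number screened is 50 / fraction, rounded up.

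| Fraction enrolling | Screened | Screened / 50 | Rate ratio 1.0 | Rate ratio 1.5 | Rate ratio 2.0 |
|---|---|---|---|---|---|
| 100% | 50 | 1.00 | 1.00 | 1.50 | 2.00 |
| 80% | 63 | 1.26 | 1.26 | 1.89 | 2.52 |
| 60% | 84 | 1.68 | 1.68 | 2.52 | 3.36 |
| 50% | 100 | 2.00 | 2.00 | 3.00 | 4.00 |
| 40% | 125 | 2.50 | 2.50 | 3.75 | 5.00 |

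For example, at 60% and a ratio of 1.5: 1.68 × 1.5 = 2.52. The range is 1.0 to 5.0.

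Two limits apply. The equal-time assumption is rough: the rest of the checklist is completed only for people with moderate to severe fatigue, so some ineligible people will take less time. And the factor does not include any loss of second-stage time, for which the protocol gives no figure.

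**The case against.** **Direction and size.** A reader might infer that many of those screened will not enrol and that the cost is certainly understated several-fold. With 1.5 to 3 people screened per enrolment and a rate 1.3 to 2 times the AHA rate, the factor would be about 2 (1.5 × 1.3 = 1.95) to 6 (3 × 2). The documents do not support this. They show that some people will not enrol, not how many, and the phone screen follows self-referral or staff referral of people already reporting fatigue. No rate is given, and the research team member's grade is not stated. Those inputs also rule out zero understatement in advance. This objection stands.

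**The AHA rate may be deliberate.** The abbreviation is not expanded, so reading it as an assistant grade is an inference. The text strips out study tasks, and the screening questions were chosen to suit usual care, so the rate could be meant as a routine-care price. That is possible, but the protocol does not say so, and it sits awkwardly with a checklist reserved for clinicians.

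**Planned data already help.** The role field, the open unit-cost column and the referral log would allow role-based pricing and a screened-to-enrolled ratio. Time per enrolled person can also be read as total time divided by the number enrolled. This stands in part: it weakens any claim that the information is absent, but no rule says whose time enters the total.

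**The initial screen may include the checklist.** The row itself attaches the word initial to the screen by existing staff and lists the checklist separately, so the narrower reading is more natural. At best the wording is unclear.

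**Comparison with face-to-face therapy.** A reader might infer that the expected cost advantage is biased. The protocol sets no comparator cost or threshold, and a face-to-face service would presumably also have to screen. That inference is not supported.

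**Conclusion.** The point holds in a limited form. The single AHA rate conflicts with the staff roles and role data elsewhere in the protocol. Second-stage checklist time is not explicitly recorded, and nothing brings the time of people who do not enrol into the cost per user. Followed as written, the screening cost per user is likely to be understated by an unknown amount. Leaving out time can only lower it, and the rate lowers it whenever screeners cost more than the AHA rate.

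The factor of 1.0 to 5.0 rests wholly on the assumed enrolment fraction (40% to 100%), the assumed rate ratio (1.0 to 2.0) and equal screening times. It concerns the screening component only. The effect on total cost per user cannot be stated, because therapist time and unit costs are not given. This is worth correcting before data collection, but it does not threaten the study.

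**What to change.** - Add a field for time taken on the second-stage checklist to the first Screening row of the costs table. Complete both screening time fields for everyone screened, including those found ineligible or who decline.
- Restate the formula: screening cost per user = sum over all people screened of (time × hourly rate of the recorded role) / number enrolled. The role field and referral log already planned supply the rest.
- If the AHA rate is meant to represent routine delivery, say so and report it as a labelled scenario beside the role-based figure.

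The cost is one extra log entry per person screened, a reworded formula, and possibly a higher reported cost per user.

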We have previously demonstrated the effectiveness of a stepped-care intervention in the Can-Sleep program for individuals with significant sleep disturbance who have received cancer treatment. Can-Sleep involves a self-directed therapeutic intervention using a self-help booklet (step 1), followed up with a CBT group for those still experiencing clinical levels of sleep disturbance (step 2). Approximately 53% of participants required step 2/CBT-Group. The purpose of the current project is to design an Australian-first, evidence-informed stepped-care CBT intervention for cancer survivors targeting fatigue, and test its feasibility.

AIMS

The overall aim of the project is to evaluate the feasibility of a stepped-care intervention that identifies and treats CRF in adults who have completed treatment for cancer.

Specific project aims:

1. To assess the feasibility and acceptability of a novel stepped-care approach to managing cancer-related fatigue.
 - a. Feasibility (e.g., adherence, recruitment and retention rate)
 - b. Acceptability (e.g., usefulness of booklet and phone calls/emails, ease of use of booklet, time spent reading booklet)
 - c. Satisfaction (e.g., perceived satisfaction with the amount of support received, extent to which program has met needs)
 - d. Proportion of people being referred to ‘STEP 2’
2. Assessment of processes, procedures and costs associated with implementing REFRESH in a clinical setting.
3. To explore whether participation in the stepped-care intervention shows promise for treatment response: improvements in fatigue, quality of life and emotional wellbeing.

PROJECT DESIGN

This project will evaluate the ‘REFRESH’ Program that aims to address problems with persistent fatigue amongst cancer survivors. Available funding is insufficient to achieve

REFRESH: Finding New Energy after Cancer

[figure not shown]
adequate power to evaluate effectiveness of the program on CRF, therefore a non-randomised design with before and after measures will be used.

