The REFRESH program is a stepped-care model (Figure 1) of up to 12-weeks duration (including completion of assessments). Participants who are experiencing moderate to severe fatigue are provided with a self-management CBT booklet to assist them with managing symptoms of fatigue and increasing energy (STEP 1). Participants have 5 weeks to work through the booklet independently. Telephone support from a Psychologist at weeks 2 and 5 and email support at weeks 1, 3 and 4 will be provided to support adherence and to address any concerns raised.

At the completion of 5 weeks, participants' fatigue symptoms will again be assessed. Those whose fatigue level does not improve significantly¹ are referred to 4 x 50 minute face-to-face/Telehealth individual or group CBT sessions with a Clinical Psychologist (PI [name]) (STEP 2).

In the Week 2 phone call, participants who have not been able to do the self-management booklet will be encouraged to engage, or fast tracked to STEP 2 for individual support as indicated (e.g., have not started booklet and/or report that they cannot complete the booklet without more support, report fatigue symptoms too distressing and interfering with ability to complete booklet).

Figure 1: Brief outline of REFRESH Stepped-Care Model

METHODS

Participants

Fifty adults who have received cancer treatment will be recruited to the study. This number is in line with our previous studies and is assessed as feasible within the timelines of the study and sufficient for a feasibility study.

¹ Less than 10-point increase on FACIT-F scale

REFRESH: Finding New Energy after Cancer

Participant Inclusion Criteria

Each participant must meet the following criteria to participate in the study:

- Aged 18 years or older at the time of recruitment
- Reports moderate to severe fatigue based on a series of screening questions administered on the phone prior to recruitment (see Appendix A).
- Is English speaking and able to read English (the intervention is only available in English)
- Cancer criteria: EITHER
 - i. Completed primary treatment for **any cancer** at least 3 months prior (to allow natural recovery)
OR
 - ii. Diagnosed with stage III or stage IV **melanoma** AND
 - is receiving maintenance treatment using a single-agent immune checkpoint inhibitor (immunotherapy) or targeted therapy AND

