- Participants will be asked for their feedback on each Chapter of the self-management booklet as they are working through STEP 1. There are approximately 5 brief questions at the end of each chapter in the booklet. These feedback questions can be removed from the booklet and sent to the research team via email or mail by participants (see TIME 1 Questionnaire PART A (T1Q-A) in Appendix A.3).
- At the completion of the week 5 phone call, participants will be emailed a link to PART B of the TIME 1 online questionnaire (or a paper copy if preferred) (T1Q-B) (see Appendix A.4).
- The FACIT-F score from the T1Q-B will determine eligibility for STEP 2. Participants with a FACIT-F score of 10 or more points higher than baseline will finish their CBT Fatigue treatment, unless they score below 34 (severe). This was established a clinically important improvement (Reddy, Bruera, Pace, Zhang, & Reyes-Gibby, 2007).
- Participants with a FACIT-F score on the T1Q-B questionnaire of less than 10 points higher than baseline and/or below 34 will be offered STEP 2. The decision to be 'stepped up' to STEP 2 will also be made in conjunction with the psychologist's clinical judgement/interview at the week 5 phone-call of STEP 1 (e.g., if questionnaire measures don't appear congruent with clinical observations of further support needs).
- Participants who do not go on to STEP 2 of the program will complete Time 2 Part B Questionnaires (T2Q-B) (see below) 6 weeks after completing the self-management booklet, with the exception of the feasibility, acceptability and satisfaction measures (which will not be applicable as they will have not completed STEP 2).

Recruitment to STEP 2: Administration of Individual CBT

[figure not shown]
- Participants eligible for STEP 2 will be offered up to 4 CBT sessions with a clinical psychologist. These sessions can be delivered one-on-one or in a small group and via face to face or via Telehealth modalities. For Telehealth sessions a secure allied health telehealth platform called CoViu (recommended by the Australian Psychology Association) or the Peter Mac telehealth platform will be utilised.

Administration of TIME 2 Questionnaires (following STEP 2)

- After the participant's last CBT session, PART A of the TIME 2 Questionnaire (T2Q-A) will be administered (either in person or via Telehealth) (Appendix A.5).

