Changes from baseline at follow-up assessments for fatigue (FACIT-F), self-efficacy (PSEFSM) and Quality of Life (Ed-5D-5L) will be analysed descriptively (means and standard deviations). This will be done separately for patients who participate in Step 1 only and for those who participate in Steps 1 and 2. Effect size estimates (i.e. standardised measures of change from baseline; in this case, mean change divided by the baseline standard deviation), as described by Kazis and colleagues, will be used to characterise the size of observed differences (Kazis, Anderson, & Meenen, 1989)

Free text items from participant questionnaires will be summarised using content analysis, whereby the content of free responses will be coded and grouped, where applicable. It is worth noting that free text items mostly accompany pre-determined response options, so it is not envisaged that all participants will opt to respond to free text items.

ETHICAL CONSIDERATIONS

This project will be conducted according to the NHMRC national Statement on Ethical Conduct in Human Research (2007 and updates) and the World Medical Association of Helsinki (2013 and updates).

Informed Consent

To ensure that participants do not feel obligated to participate, the study team will ensure invitees that participation is voluntary and that they may stop their involvement in the project at any time. The study team will explain that their decision will not impact on their care or their relationships with hospital staff.

REFRESH: Finding New Energy after Cancer

Data storage and privacy issues

A unique study identification number system will be used for all data collection for this project. This system will employ the use of paired tracking numbers, so identifiable participant information (e.g., name, date of birth) and participant contact details (e.g., email and phone number) is kept separate from questionnaire responses. Therefore, participant's personal details cannot be linked with their research involvement and questionnaire responses unless you have access to the paired tracking numbers, which will be stored in an electronic password protected excel spreadsheet that is only accessible by the research team.

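### Change scores for Aim 3 are summarised by step reached, but the T1 FACIT-F change largely decides the step, and no all-participant summary is stated

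*Protocol*

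**What the plan says.** AIMS, item 3, is framed for the programme as a whole: "To explore whether participation in the stepped-care intervention shows promise for treatment response". Evaluation, item 4, calls these outcomes exploratory and underpowered, but intends them as preliminary data for a later effectiveness study.

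Data Analysis covers "Changes from baseline at follow-up assessments for fatigue (FACIT-F), self-efficacy (PSEFSM) and Quality of Life" and summarises them by means and standard deviations. It then says "This will be done separately for patients who participate in Step 1 only and for those who participate in Steps 1 and 2". The effect size is "mean change divided by the baseline standard deviation", and the text does not say whether that SD comes from the group or from all participants. No change summary for all participants together is stated.

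Administration of TIME 1 Questionnaires says how the groups arise: "The FACIT-F score from the T1Q-B will determine eligibility for STEP 2". For those who stop after the booklet, the rule reads "Participants with a FACIT-F score of 10 or more points higher than baseline will finish their CBT Fatigue treatment"; an exception is made for scores under 34. On the other side are those with a score "less than 10 points higher than baseline and/or below 34 will be offered STEP 2". Three other things move people: the psychologist's judgement at the week 5 call, whether the offer of STEP 2 is taken up, and the week 2 route by which a participant may be "fast tracked to STEP 2 for individual support as indicated" (PROJECT DESIGN).

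**The concern.** The two groups are formed after baseline, mainly on the outcome that is then summarised within them. High T1 changes, whether from benefit or from measurement variation, are sorted into one group and low ones into the other. Neither group's mean change estimates what the booklet, the CBT sessions or the programme does.

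The 10-point gain that ends treatment is also the gain that Intervention Impacts (Outcomes) calls clinically significant. A group selected by the rule therefore meets the success criterion by definition.

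At stake is the figure carried into the next study. If an effect size is taken from either row, planning would start from a number that selection has pushed up (Step 1 only) or down (Steps 1 and 2 at T1).

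**Working it through.** **The plan's own figure.** The section on STEP 2 expects 50 × 0.50 = 25 participants to qualify for it. With the 53% quoted for the earlier sleep programme it would be 50 × 0.53 = 26.5. So the protocol expects roughly an even split.

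**What follows from the rule alone.** Each participant who finishes under the rule has T1 − T0 ≥ 10, so the group mean is at least 10. The effect size with a common SD is at least 10/SD. For assumed SDs of 12, 10 and 8 this is 0.83, 1.00 and 1.25. No assumption about benefit enters.

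**Simulation.** Inputs from the protocol: FACIT-F range 0 to 52, and finish after Step 1 if the gain is ≥ 10 and the T1 score is ≥ 34. Assumptions, because the protocol gives no values: baseline mean 26 or 30, SD 10, correlation 0.6 to 0.8 between any two visits, the same true gain for everyone at T1 and T2, no added effect of STEP 2, and everyone placed by the rule. Scores were drawn as normal, rounded and clipped, with 400,000 participants per scenario. Mean FACIT-F change at T1:

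| True gain | Share in Step 1 only | Step 1 only | Steps 1 and 2 | All |
|---|---|---|---|---|
| 0 | 3% to 9% | +12.4 to +14.7 | −1.5 to −0.4 | 0.0 |
| 4 | 10% to 19% | +13.1 to +15.6 | +1.2 to +2.9 | +3.9 to +4.0 |
| 12 | 46% to 51% | +15.4 to +17.8 | +4.9 to +8.1 | +11.2 to +11.6 |

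The row with a true gain of 12 matches the expected split. Its pooled value is a little under 12 because of the ceiling at 52.

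Arithmetic check (mean 26, correlation 0.7, true gain 12): 0.460 × 16.9 + 0.540 × 7.1 = 7.8 + 3.8 = 11.6, the pooled change.

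**Choice of divisor.** With no true change, the Step 1 only effect size is 1.3 to 1.5 using the all-participant SD and 2.2 to 2.4 using the group's own. The group's own baseline SD is only about 5.4 to 6.3, against 9.9 for everyone. On the own-SD reading the result stays at 2.2 to 2.4 for true gains of 0, 4, 8 and 12, so it hardly responds to the truth.

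**T2 and the other outcomes.** The floor of 10 does not apply here, but selection carries over through correlation. With no true change, FACIT-F at T2 is +5.4 to +6.1 in Step 1 only and −0.6 to −0.2 in the other group. For a second outcome whose change correlates 0.5 with FACIT-F change (assumed; baseline mean 25 to 30, SD 8 to 12, visit correlation 0.5 to 0.7), the T1 effect sizes are 0.69 to 0.83 and −0.08 to −0.03 when the truth is zero.

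**Departures from the rule.** Placing 10% or 20% of participants against the rule at random (mean 25, SD 10, correlation 0.6, no true change) cuts the Step 1 only effect size from 1.49 to 0.50 or 0.23. With a true gain of 5 points (pooled effect size 0.50) it falls from 1.60 to 1.14 or 0.87.

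**The case against.** The strongest reply is that the analysis is descriptive, in a study whose main purpose is feasibility. No test, between-group comparison or go/no-go rule uses these effect sizes, and reporting by pathway is natural in stepped care. The two groups cover everyone, so a reader with group sizes and means can recover the pooled mean, as the arithmetic check shows. A separate analysis plan may add that row. All of this stands, and it limits the severity. It does not remove the bias: the one presentation the protocol fixes is a split on the outcome, with no stated summary that matches Aim 3.

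A reader might infer four stronger things, which the document does not support.

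- *A large Step 1 effect would appear even if nothing worked.* With no true change only 3% to 9% of participants, about 1.5 to 4.6 of 50, would finish at Step 1. Almost everyone else would be offered STEP 2, so a few decliners would swamp them. Group sizes beside the means would expose this.
- *The plan reports a spurious gain from STEP 2.* T1-to-T2 change is not a planned statistic. With no true change it would be under 1 point. It reaches about 2 to 3 points at a true gain of 12, and then only if a reader subtracts one planned row from another.
- *The results for self-efficacy, EQ-5D-5L and T2 are fixed in advance.* Only FACIT-F at T1 has a floor. For the rest the size of the bias rests on correlations the protocol does not give.
- *Pooling gives the programme's effect.* It does not. The study has no control group and enrols people screened for fatigue, so natural recovery and regression to the mean stay in the pooled change. The simulated pooled value of 0.0 leaves both out.

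**Conclusion.** The concern holds for exploratory Aim 3 and should be fixed; it does not touch the feasibility outcomes. Certain from the text: the step groups are formed mainly on T1 FACIT-F change, the Step 1 only mean at T1 is at least +10 for those placed by the rule, the divisor SD is not identified, and no all-participant change is stated.

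The size is illustrative. At the split the protocol expects, the by-step T1 means lie roughly 4 to 6 points either side of the pooled change, on a 0 to 52 scale with a 10-point criterion (for example 16.9 − 11.6 = 5.3 above and 11.6 − 7.1 = 4.5 below). This rests on the assumed mean, SD and correlations, on a gain common to all, and on everyone following the rule. Clinical judgement, fast-tracking and declined offers would shrink it.

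**What to change.** In Data Analysis:

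- Make the main Aim 3 summary the change from baseline in all enrolled participants with available data, T0 to T1 and T0 to T2.
- Use the all-participant baseline SD as the divisor for every effect size.
- Keep the by-step tables as secondary, with group sizes, labelled as selected on the T1 score and not as effect estimates of either step.
- State that the pooled change is an uncontrolled before-after change, and that T0 to T1 includes any participants fast-tracked at week 2, so it is not purely a booklet phase.

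The stepping rule itself need not change for this. The cost is one paragraph, a few table rows and no new data. The trade-off is a less favourable headline effect size than Step 1 only would have shown.
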